Participants and Power. We will test 150 participants (N=25/condition). The sample size was selected so that multiple regression analyses with all predictors have high power ($1-\beta=0.8$, $p<0.05$, two-tailed) to detect even a small (Cohen's $f^2=0.08$) reliable deviation from 0 of a single linear regression coefficient (G*Power). This sample size is twice that of previous laboratory incidental L2 training studies (N=13, 80; N=10, 63), appreciating that we will need a somewhat larger sample to accommodate the potential for attrition across the retention interval. Even if we were to experience as much as 33% attrition, this sample size will assure a robust test (N=17; Cohen's $f^2=0.08$; power=.6) in line with prior research.

All participants will be native-English young adults (18-28 years) with normal hearing, no history of speech or language disorder, no prior experience with a tonal language, and background in musical training equated across groups. Half of the participants will be enrolled in first-year Mandarin at CMU (+instruction). The other half will be enrolled in first-year Spanish or French at CMU (-instruction). First-year Mandarin, Spanish, and French language courses are offered in Fall and Spring terms with 100 students completing each of these courses in 2017-2018. Instructors of each language group make use of the same, shared lesson plans and undergo thorough training to ensure uniformity. Our plan is to recruit participants across four academic semesters, presenting an excellent participant pool with the majority of enrolled students meeting inclusion criteria in recent semesters.

Protocol Details Common to All Participants. Pre-test Measures. Participants from each of the six groups (**Table I**) will undergo language, sensory, and cognitive assessments to examine factors that may interact with learning. Online Battery of Questionnaires. We will document participants' language background, dominant hand, musical training, and self-reported history of language

Carnegie Mellon University

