disorders, speech impairments, videogame expertise, and self-reported hearing loss using batteries established by prior research. *Basic Hearing Screening*. We will measure participants' pure-tone frequency thresholds using the adaptive maximum likelihood procedure as implemented in the MLP MATLAB toolbox, which converges quickly (~30 trials). *Cognitive Tests*. Since auditory working memory and phonological ability are associated with language learning, we will use the Woodcock-Johnson Tests of Oral and Cognitive Abilities to evaluate phonological awareness, working memory and auditory working memory using the Sound Blending, Numbers Reversed and Auditory Working Memory subtests, as in prior research. These tests will be administered before training and/or classroom instruction commences to accommodate exclusion criteria and to match groups on music training. Pre-test measures will allow assessment of group differences and individual scores will be used as regressors in analyses to examine the relationship of individual differences to learning outcomes using linear mixed-effect regression models in R to capture both fixed effects of linguistic/cognitive background and training, as well as the random effects of participant.

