Measures to Assess Learning. Whereas +instruction learners will have been explicitly instructed in Mandarin tone in the classroom, -instruction listeners will not. This marked difference impacts the methods available to assess learning, in part because naïve listeners cannot overtly label the tones. To meet this challenge, we employ three assessments that do not depend upon explicit knowledge. *(1) Perceptual Tasks: Pitch Pattern Discrimination (PPD) and Pitch Direction Identification (PDI) Tests.* Prior research has shown that participants who exhibit good Mandarin tone learning tend to exhibit better sensitivity to F0 contours in pitch contour discrimination and identification tests. These two measures will allow us to ascertain pre- to post- and delayed post-test change in Mandarin tone perception in a manner that can be readily applied across +/- instruction groups, and to assess perceptual weighting of pitch contour versus pitch height (and its change with learning). Additionally, these tests provide an assessment of individual differences in F0 sensitivity (pre-test). The PPD and PDI tests will follow the approach of our prior research. We will use the PPD data to calculate the sensitivity (d') and reaction time (offset of the second stimulus to response) of each participant at pre-test, post-test (after instruction/training), delayed post-test (3 months after training). We will use multidimensional scaling (MDS; Individual Differences Scaling, INDSCAL) with the PPD data to examine the underlying perceptual dimensions listeners use to discriminate tone contours. This MDS approach models successful prior research and provides us with a perceptual metric of the impact of learning across groups that do not depend on explicit awareness of tone. We will use the PDI data to calculate accuracy for each participant at pre-test, post-test, and delayed post-test.

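### PPD and PDI learning is framed as change from pre-test, with no adjustment for each outcome's own pre-test score, so training-arm contrasts may be less precise than the data allow

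*Combined protocol and SAP*

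**What the plan says.** In the combined protocol and SAP, 'Measures to Assess Learning', item (1), the purpose given for PPD and PDI as learning outcomes is: "These two measures will allow us to ascertain pre- to post- and delayed post-test change in Mandarin tone perception". The section then lists what is computed. For PPD: "We will use the PPD data to calculate the sensitivity (d') and reaction time", at pre-test, post-test and a delayed post-test three months after training. For PDI: "We will use the PDI data to calculate accuracy for each participant at pre-test, post-test, and delayed post-test". These are scores per visit. No difference score is defined and no model for the training effect is written out. The same section gives the pre-test scores a second role, as a measure of individual differences in F0 sensitivity.

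'Protocol Details Common to All Participants' plans linear mixed-effects models with fixed effects of background and training and a participant random effect. It says that "individual scores will be used as regressors in analyses to examine the relationship of individual differences to learning outcomes". That sentence follows the questionnaires, the hearing screen and the cognitive tests, and does not mention PPD or PDI.

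'Participants and Power' gives the size: "We will test 150 participants (N=25/condition". It also considers 33% attrition, which leaves 17 per condition.

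**The concern.** The question is how the nonspeech, speech and no-training arms will be compared on PPD d', PPD reaction time and PDI accuracy. Subtracting the pre-test score fixes its coefficient at 1, so all the pre-test measurement noise passes into the outcome. Entering the pre-test as a covariate lets the data choose the coefficient that leaves least residual variance.

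The planned mixed model does not settle this. With complete data and unconstrained baseline means, the visit-by-group term is the between-arm difference in mean change, so it has the change-score precision.

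With 25 per cell, or 17 under the plan's attrition scenario, the lost precision raises the chance of missing a real training benefit. Leaving the estimator open also allows it to be chosen after the data are seen.

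**Working it through.** **The plan's own power figure.** 'Participants and Power' claims power 0.8 to detect a "reliable deviation from 0 of a single linear regression coefficient (G*Power" at f² = 0.08, two-sided 5%. With noncentrality √(f²N) and N−p−1 degrees of freedom, N = 150 gives 0.93, and N = 101 is enough for 0.80, for any number of predictors p from 1 to 15. The stated figure is therefore not reproduced. That is a separate matter: the calculation involves no pre-post correlation and does not bear on this point.

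**Inputs.** From the documents: six cells of 25, so 25 v 25 within an instruction level and 50 v 50 pooled over instruction; 17 per cell after 33% attrition, so 34 v 34 pooled; two-sided 5%. Assumed, because the documents give no value: pre-post correlation rho from 0.3 to 0.9, and a true arm difference of 0.5 SD of the post-test score.

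**Variances, equal SDs at both visits (post-test variance = 1).**
- Change: 2(1−rho).
- Adjusted for pre-test: 1−rho².
- Ratio, adjusted to change: (1−rho²)/[2(1−rho)] = (1+rho)/2.

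**Power.** Two-sided noncentral t, noncentrality (0.5/σ)√(n/2), 2n−2 degrees of freedom, with σ the square root of the relevant variance. At rho 0.5, σ is 1.000 for change and 0.866 for adjusted. At n = 25 the noncentralities are 1.77 and 2.04; at n = 50 they are 2.50 and 2.89.

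| rho | variance ratio | 25 v 25, change → adjusted | 50 v 50 | 34 v 34 |
|---|---|---|---|---|
| 0.3 | 0.65 | 0.31 → 0.44 | 0.55 → 0.74 | 0.40 → 0.57 |
| 0.5 | 0.75 | 0.41 → 0.52 | 0.70 → 0.82 | 0.53 → 0.65 |
| 0.7 | 0.85 | 0.61 → 0.68 | 0.89 → 0.93 | 0.75 → 0.81 |
| 0.9 | 0.95 | 0.97 → 0.98 | both above 0.99 | both above 0.99 |

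At 17 v 17 and rho 0.5 the same formula gives 0.29 → 0.37. Removing one degree of freedom for the covariate moves the adjusted figures by no more than about 0.001.

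**Unequal SDs.** Let k be pre-test SD divided by post-test SD. The change variance becomes 1+k²−2·rho·k, and the ratio is (1−rho²)/(1+k²−2·rho·k).
- rho 0.7, k 0.8: 0.51/0.52 = 0.98, almost no gain.
- k = rho: the denominator is 1−rho², so the ratio is exactly 1.
- rho 0.7, k 1.25 (post-test spread shrinks): 0.51/0.8125 = 0.63, a larger gain.

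The ratio never exceeds 1, because change is the special case in which the coefficient is held at 1.

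**The case against.** A reader might infer that the plan has chosen an unadjusted change-score analysis. The documents do not support that. The sentence about change describes what the tests are for, and the quantities actually listed are scores at each visit. A baseline covariate or a mixed model with constrained baselines would fit the same text. A reader might also infer that pre-test scores serve only to study individual differences. That goes too far as well: the planned models contain training effects, and pre-test PPD and PDI are named as individual-difference measures, so a model holding both is possible. What stands is that the text never says so for these outcomes, and its one sentence on regressors is attached to other tests.

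The size of the gain is also open to challenge. Rho and the 0.5 SD effect are assumptions, and the simple ratio needs equal SDs. The 50 v 50 figures average over any interaction between instruction and training. These points limit how large a gain can be promised. They do not make adjustment worse than change beyond the one degree of freedom.

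The most serious objection concerns allocation. 'Protocol Details Specific to +instruction Learners' mentions assignment, and other sections mention matching on music training, but randomisation to training arms is never stated. Without it, adjusted and change analyses can estimate different quantities, and precision alone does not decide between them. This stands as a condition on the fix.

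**Conclusion.** The point holds as a gap with a calculable cost: PPD and PDI learning is framed as change, no estimator is given, and no adjustment for the outcome's own pre-test is specified. If the contrasts are run as change or as a free-baseline visit-by-group term, the adjusted analysis would have 5% to 35% less variance for rho from 0.9 to 0.3 under equal SDs. The saving is close to nothing where post-test spread is wider and k is near rho. At rho 0.5 and a 0.5 SD effect, the gain is about 0.11 to 0.12 in power at 25 v 25 and at 50 v 50.

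The conclusion is confined to training-arm contrasts within or stratified by instruction level, and assumes that those arms differ at pre-test only by chance. It does not extend to the +/−instruction contrast. That contrast is set by course enrolment, so adjustment could change what is being estimated.

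**What to change.** State in the SAP that, for contrasts among nonspeech, speech and no training on PPD d', PPD reaction time and PDI accuracy, the post-test and delayed post-test scores are modelled with the participant's own pre-test score on the same measure as a covariate, within or stratified by instruction level. Report change scores descriptively. Keep the change analysis for the +/−instruction contrast.

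State how participants are assigned to training arms. If assignment is not random, report the change analysis of the training contrasts as a sensitivity check.

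The cost is SAP wording and one degree of freedom per outcome. No new data are needed, since the pre-test is already collected in all six groups. The remaining downside is the assumption of chance-only pre-test differences between training arms, which the statement on assignment should address.

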Carnegie Mellon University

Study Protocol and Statistical Analysis Plan (SAP)

NCT04509024

Incidental Auditory Category Training for Language Learning

1R03HD099382-01

February 26, 2024

Carnegie Mellon University

Design Overview. We propose an 8-week training study among university students with no prior experience with Mandarin (or any tonal language). We will track learning through two modalities: explicit classroom instruction and web-based incidental training. Half of the participants will come

Table I	Incidental, Nonspeech (nonspeech)	Explicit, Speech (speech)	No Training (none)
Relevant Classroom, Mandarin L2 (+instruction)	+ instruction / nonspeech Preliminary Study 2	+ instruction / speech Preliminary Study 2	+ instruction / none
Irrelevant Classroom, French/Spanish L2 (-instruction)	- instruction / nonspeech Preliminary Study 1	- instruction / speech Prior literature	- instruction / none

from first-year Mandarin classes at Carnegie Mellon University (CMU). These students (+instruction, see **Table I**) will undergo traditional L2 learning through explicit instruction, as is the typical pedagogical approach of university classrooms. This approach emphasizes the four specific tonal contours and the lexical role of tone in Mandarin word recognition through explicit instruction. On average, these students will spend 200 minutes/week in classroom instruction, and an additional 300 minutes expected preparation outside of class. The other half of the participants will be recruited from the same university-student population, but will be engaged in non-Mandarin, non-tonal foreign language instruction for Spanish or French at an identical 200 minutes/week. In this manner, these participants (-instruction, **Table I**) will be similarly motivated to learn a foreign language, yet will have no tonal training: they will not be taught the four tone categories or the lexical role tone carries. In this way, the -instruction group models naïve participants typical of laboratory L2 training studies, with the added control of being an equally motivated cohort. Participants will undergo either supplementary incidental nonspeech training or supplementary explicit speech training. A third group will serve as a control and undergo no additional training.

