(2) Artificial language-learning task. Previous research from our team has demonstrated the feasibility of using an artificial Mandarin-like tonal language to track and test learning across speakers with different levels of overt awareness of Mandarin tone, such as learners early in explicit classroom instruction (+instruction) compared to naïve learners (-instruction). PI [name] designed an artificial language that mimicked Mandarin's linguistic characteristics, including identical tone contours and syllable structures, but remained unintelligible to both English and Mandarin speakers. Because the artificial language was modeled on Mandarin, the results revealed not only how native speakers represent new Mandarin-like words, but also how non-native L2 learners acquire Mandarin-like tones in the context of the language acquisition task. In this multi-day

Carnegie Mellon University

training and testing paradigm, participants learn 130 consonant-vowel syllable+tone nonce words, each paired with a black and white nonce symbol. Daily learning is assessed through a 4-alternative forced choice (4AFC) task in which participants hear a target syllable+tone and click on a symbol. Feedback guides learning. This study also provides a way to compare online tonal sensitivity across Mandarin L2 learners and naïve learners with no prior experience with tone.

Protocol Details for Incidental Nonspeech Training. Training will take place in the videogame paradigm. Participants will train 60 min/week across 8 weeks for a total of 8 hours, online at their convenience. Our prior research demonstrates that overall time-on-task is closely related to the number of stimulus exposures in the videogame, even though participants differ in ultimate *gaming* achievements like Highest Level achieved. This is because at higher, faster levels "trials" are shorter with fewer stimulus repetitions, but there are more of them. Thus, our principal concern is with time-on-task and not with equating experience across listeners, *per se*. Protocol compliance will be monitored electronically and regular contact with our research team will be tailored to encourage high retention, as has been successful in our prior research. Learners will train on a set of nonspeech hums derived from a larger set of Mandarin talkers (N=20 instead of N=4 in Preliminary Study 2).

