The training regimen we propose is substantially longer (8 hrs over 8 wks) than has been investigated in prior studies of incidental auditory category learning (~2.5 hrs in 5 days; 62). *This presents the opportunity to take a data-intensive approach.* We will use the continuous, fine-grained online data generated in the videogame to address the fundamental question of how categories are formed via incidental learning.

Protocol Details for Web-based Speech Training. Groups undertaking explicit speech training also will train 60 min/week across 8 weeks for a total of 8 hours. Training sessions will be broken into 20-minute modules, each of which takes place online. Protocol compliance will be monitored electronically and regular contact with our research team will be tailored to encourage high retention. Explicit speech training groups will train on standard L2 audio-lingual materials, which aim to develop learners' phonological awareness of tone. These tasks include same/different tone discrimination, AXB discrimination, 2-alternative-forced choice, 4-alternative-forced-choice, and tone labeling (roughly 4 minutes per task). Though the tasks are currently designed to be used by students enrolled in the university curriculum, all tasks are purely perceptual and do not require linguistic knowledge. For example, a participant must perceive *ma1* and *ma3* as different sounds but not necessarily understand that the former means 'mother' and the latter means 'horse.' As a result, the participants in the -instruction condition can perform the tasks without explicit knowledge of Mandarin. The stimuli will be modified to include speech from 20 speakers (thus matching the nonspeech hum stimuli). In addition to task accuracy, we will track time-on-task.

Protocol Details Specific to +instruction Learners. *Classroom Metrics.* We will collect metrics that include class attendance, self-reported study time, and self-reported classroom social network and interaction with Mandarin speakers. These metrics will allow us to compare and control for potential differences that may arise between +speech and +nonspeech groups. Importantly, the classroom instructor will be blind to each participant's assignment so as not to affect his/her performance. *Mandarin Tone Production.* Whereas -instruction, nonspeech learners train on perceptual representations relevant to Mandarin tone, they never explicitly encounter Mandarin

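### Should the classroom metrics also be compared with the untrained Mandarin arm, in case both training programmes displace study time equally?

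*Combined protocol and SAP*

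**What the plan says.** The Classroom Metrics paragraph, under Protocol Details Specific to +instruction Learners, lists what is collected: "We will collect metrics that include class attendance, self-reported study time, and self-reported classroom social network and interaction with Mandarin speakers". It then states the purpose: "These metrics will allow us to compare and control for potential differences that may arise between +speech and +nonspeech groups".

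The training load of the two named arms is the same. For nonspeech training: "Participants will train 60 min/week across 8 weeks for a total of 8 hours, online at their convenience". For speech training: "Groups undertaking explicit speech training also will train 60 min/week across 8 weeks for a total of 8 hours".

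Table I in the Design Overview has a third Mandarin arm, +instruction/none, and the text under it says: "A third group will serve as a control and undergo no additional training". The same section gives Mandarin students 200 minutes a week in class and "an additional 300 minutes expected preparation outside of class", which I read as a weekly figure. Of the French and Spanish students it says "they will not be taught the four tone categories or the lexical role tone carries".

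No section names the +instruction/none arm in a comparison of classroom metrics. The group comparisons described with the pre-test measures concern data taken before training starts, so they do not cover this point.

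**The concern.** The plan names the one pair of Mandarin arms that is matched on added training time. It leaves out the pairs that differ on it by design, at 60 against 0 minutes a week. Sixty minutes is a fifth of the expected preparation time, so some students might count training as study and do less of the latter. If both trained arms did this equally, the named comparison would show nothing.

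What would be at stake is interpretation. Suppose trained Mandarin students gained little over +instruction/none. The named comparison could not tell training that adds little from training that adds something while replacing Mandarin study. Any comparison of the training gain between Mandarin and French or Spanish students would also be touched, because study displaced among the latter carries no tone content.

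**Working it through.** The plan states no figure on this point, so there is none to reproduce.

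**Inputs from the documents.** Training is 60 minutes a week for 8 weeks in both trained arms (60 × 8 = 480 minutes = 8 hours, as stated) and 0 in the control. Expected preparation is 300 minutes, read as weekly. There are 25 participants per condition, or 17 after 33% attrition.

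**Assumptions, not in the documents.** Displacement is 30 minutes (half) or 60 minutes (full) a week, equal in both trained arms. The SD of weekly study time is 120 to 240 minutes. One SD of study time moves the outcome by 0.3 SD. The training effect before displacement is 0.80 SD.

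**1. Does a shared change cancel?** Let b be usual study time and s the shared change.
- Speech minus nonspeech: (b + s) − (b + s) = 0.
- Trained minus none: (b + s) − b = s.

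So the named pair cannot show a shared change. A change confined to one trained arm would show there in full. Training is 60/300 = 20% of expected preparation.

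**2. What would displacement do to the outcome?** Full displacement is 60/120 = 0.5 SD to 60/240 = 0.25 SD of study time. Times 0.3, this lowers the trained v none difference by 0.15 to 0.075 SD. Half displacement lowers it by 0.075 to 0.0375 SD. Power of a two-sided 5% t test, 25 v 25:

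| Scenario | Difference (SD) | Power |
|---|---|---|
| No displacement | 0.80 | 0.79 |
| Half, SD 240 | 0.7625 | 0.75 |
| Half, SD 120, or full, SD 240 | 0.725 | 0.71 |
| Full, SD 120 | 0.65 | 0.61 |

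**3. What would it do to a comparison of training gains across languages?** With 50 v 25 in each language, the SE is √[2 × (1/50 + 1/25)] = √0.12 = 0.346 SD. A false difference of 0.075 to 0.15 SD is 0.2 to 0.4 SE, so a nominal 5% test rejects with probability 0.055 to 0.07.

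**4. Would the added comparison answer the question?** The 95% half-width is t(0.975, df) × √(1/n₁ + 1/n₂).

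| Trained v none | Half-width (SD) | At SD 120 | At SD 240 |
|---|---|---|---|
| 50 v 25 | 1.99 × 0.245 = 0.49 | ±59 min | ±117 min |
| 34 v 17 | 2.01 × 0.297 = 0.60 | ±72 min | ±143 min |

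Even if the observed difference were exactly zero, the interval would barely exclude a 60-minute displacement in the most favourable cell and would not exclude it in the other three. Power to detect half displacement (0.125 to 0.25 SD) at 50 v 25 is 0.08 to 0.17. For full displacement at SD 120 (0.5 SD) it is 0.52.

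**The case for a change.** The best case for a change is that it costs almost nothing. One sentence and one table would extend the comparison to all three Mandarin arms, probably with no new data, and an interval tells the reader more than no comparison. The sponsor already treats classroom exposure as worth comparing, and the pair it names is the one least able to reveal a shared effect of training. The reading of the text and the arithmetic behind this both stand.

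The need for the change does not. The sentence on the metrics says what they make possible; it does not restrict them to two arms. Naming speech and nonspeech is understandable, since Table I marks those two Mandarin arms as the Preliminary Study 2 pair. Exactly equal displacement is also a special case. One programme is a videogame with hums and the other uses audio-lingual exercises designed for enrolled students, so the two could well replace study to different degrees, and that difference would show in the named pair. The remark about training at a convenient time is made only for the nonspeech arm.

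A fuller remedy, adding study time to the trained v none model, has a cost of its own. Study time is measured after assignment and may be a consequence of training, so adjusting for it changes the question from the total effect of adding training to something narrower. Such a model could only be exploratory.

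**Conclusion.** No change is needed. The trained v none comparison still estimates the total effect of adding training to a Mandarin course, whether or not study time shifts, and that effect is not biased. What is missing is a descriptive comparison that the metrics section already supports and that an analyst would reasonably tabulate for all three arms, counting study time without training minutes. Doing so is optional.

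The possible harm is limited to interpretation. On the assumed values it is a loss of about 0.04 to 0.15 SD in the trained v none difference. The fall in power to 0.61 requires full displacement in both arms, the smaller assumed SD and the 0.3 slope together. These sizes rest on assumptions, because the documents give no study-time SD, no link between study time and outcome, and no evidence that training displaces study. The conclusion rests less on those values than on two points: the total effect is unbiased, and an interval of ±0.49 SD at full enrolment would usually leave the two explanations of a small gain unseparated.

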in the course of training. Thus, it is not possible to elicit Mandarin tone speech productions among -instruction learners. (However, speech production measurements will be possible in the Artificial Language Learning task administered post-training. This provides an across-group assessment of tone production). But, since all +instruction learners are instructed explicitly in Mandarin tone within the classroom environment it is possible to examine their tone productions across the course of the study. We will elicit speech productions from +instruction participants following the approach taken in Preliminary Study 2 using native-Mandarin raters, with associated acoustic analyses of the F0 contour to characterize these speech productions.

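### Does the unstated order of the artificial-language task and the PPD/PDI tests compromise the untrained control cell?

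*Combined protocol and SAP*

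**What the plan says.** Under *Measures to Assess Learning*, PPD and PDI are given at pre-test, "post-test (after instruction/training), delayed post-test (3 months after training"). Their purpose is stated there: "These two measures will allow us to ascertain pre- to post- and delayed post-test change in Mandarin tone perception".

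The artificial-language task is the second assessment under the same heading. It is described through the team's earlier work as a multi-day "training and testing paradigm, participants learn 130 consonant-vowel syllable+tone nonce words". The language was modelled on Mandarin, "including identical tone contours and syllable structures", and the daily four-choice task is not passive: "Feedback guides learning". The number of days planned for this study is not given.

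The task's timing appears only in a parenthesis on tone production, under *Protocol Details Specific to +instruction Learners*: "speech production measurements will be possible in the Artificial Language Learning task administered post-training". The same parenthesis presents it as a way to compare production across groups, and no cell is exempted.

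*Design Overview* says of the -instruction participants that they "will have no tonal training: they will not be taught the four tone categories or the lexical role tone carries". Of the no-training condition it says: "A third group will serve as a control and undergo no additional training".

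**The concern.** An assessment that teaches can change what is measured after it. Table I shows that -instruction/none (25 of 150 planned participants) is the only cell with neither Mandarin instruction nor supplementary training. If its members learn tone words with feedback before a PPD/PDI session, that session no longer shows performance without tone training. The task's four-choice format also resembles one of the exercises in the explicit speech arm.

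Read naturally, post-training suggests the end of the 8 weeks, which is before a test set 3 months later. Change from post-test to delayed test would then mix forgetting with new learning. The trained-versus-untrained gap among -instruction learners could shrink if controls catch up, or widen if trained listeners gain more from the task. If the task also came before the immediate session, no post-training measurement would be free of it.

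**Working it through.** The plan gives no figure on this point to reproduce. Its power statement does not concern test order. The check is therefore what each possible order would do to each contrast.

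**Notation.** For group g, let P be the mean immediate post-test score without the task, F the loss over 3 months, and A the shift in PPD/PDI caused by the task. T is a training group and N the matching no-training group. For simplicity, A is taken as lasting once acquired.

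| Order | Immediate contrast, T − N | 3-month contrast, T − N |
|---|---|---|
| PPD/PDI, 3-month PPD/PDI, task | P_T − P_N | (P_T − P_N) − (F_T − F_N) |
| PPD/PDI, task, 3-month PPD/PDI | P_T − P_N | (P_T − P_N) − (F_T − F_N) + (A_T − A_N) |
| Task, PPD/PDI, 3-month PPD/PDI | (P_T − P_N) + (A_T − A_N) | (P_T − P_N) − (F_T − F_N) + (A_T − A_N) |

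1. All three orders fit the stated timing, because the 3-month session is also after training.
2. In the first order nothing is affected. In the second the immediate contrast is clean. Only the third touches both.
3. Where the task does precede a test, every group has taken it. If the groups gain equally, A_T − A_N = 0 and the contrast is unchanged. If not, the contrast is still a valid comparison of groups under one test sequence. It is then the difference remaining after everyone has done the task.
4. Within one group, change from post-test to delayed test in the second order is −F + A, so it is not forgetting alone. The plan defines no analysis that needs it to be. Retention is named once in *Participants and Power*, where it justifies the sample size against attrition.
5. The statement about tonal training in *Design Overview* covers all -instruction participants and is explained by what the classroom omits. Two of the three -instruction cells then receive nonspeech or speech training, so it cannot promise freedom from tone exposure throughout the study. The control is defined by the absence of additional training, and an assessment given to all six cells does not breach that.

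**Size.** The documents give no value for A, so power can only be illustrated. Assume a true gap of 0.80 SD, of which the task closes a share c among -instruction learners only. Use a two-sided 0.05 noncentral t test with n = 25 per cell, df = 6 × 25 − 6 = 144 and no baseline covariate.

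- One training cell against none, -instruction only: difference 0.8(1 − c), SE = √(2/25) = 0.283.
- The same, pooled over instruction: difference 0.8(2 − c)/2, SE = √(1/25) = 0.20.

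| c | -instruction only | Pooled |
|---|---|---|
| −25% (gap widens) | 0.94 | 0.99 |
| 0 | 0.80 | 0.98 |
| 25% | 0.56 | 0.94 |
| 50% | 0.29 | 0.85 |
| 75% | 0.11 | 0.70 |

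The spread comes entirely from the assumed 0.80 SD and c. It shows that power depends on effect size, not that this study loses any. Nor is the two-cell contrast a stated analysis: the plan describes multiple regression and mixed-effect models, with pre-test scores as regressors.

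**The case for a change.** The best argument for a change is that equal exposure need not give equal gains, and that this document is both protocol and SAP. Recruitment spans four semesters, so without a written order the sequence could drift between cohorts, and the delayed contrast would then not have one meaning. One sentence would close the gap without extra participants or visits. The plan's own account of the task as one in which learners acquire tones supports treating it as exposure.

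Part of this stands. The order is not written down, and a report of the 3-month results should say whether the task had already been done. But drift between cohorts is conjecture, and so is transfer from learning symbol–word pairs to pitch discrimination or direction scores. PPD and PDI are described as pre- and post-training measures of change, so giving them before a multi-day learning task is the obvious way to run the post-test. Nothing suggests the team would do otherwise, although nothing in the text confirms it. Moving the task beyond the 3-month test would not be a clear gain either, since it would expose that outcome to the attrition the plan allows for (up to 33%).

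**Conclusion.** No change is needed. The document leaves a scheduling detail unstated, but no rule it does state gives a wrong result. If the perceptual tests are run first at post-test, the immediate training-versus-none contrast is free of the task. If the task then precedes the 3-month session, the delayed contrast is analysed in the same way and is read as the difference remaining after all groups have done the task.

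This rests on two assumptions: that all six cells take the task in the same position, which its use as a comparison across groups implies, and that the team gives PPD and PDI before it at post-test. If the second failed, both post-training contrasts would carry the term A_T − A_N. They would still be valid comparisons between groups, but no longer comparisons with a cell free of tone exposure. The documents do not show that this happens, and they do not allow its size to be estimated.
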